9.1. ADVERSE EVENT (AE)

An adverse event (AE) is defined as any unfavorable or unintended sign, symptom, or disease that occurs or is reported by the patient to have occurred, or a worsening of a pre-existing condition. An adverse event may or may not be related to the study treatment.

AEs will be elicited through direct questioning and subject reports. Any abnormality in physical examination findings or laboratory results that the investigator believes is clinically significant (CS) to the research subject and that occurred after initiation of the first study treatment will be reported as AEs. Abnormal findings that are NOT clinically significant should not be recorded as an AE.

9.2. REPORTING OF ADVERSE EVENTS

Report initiation for all AEs and SAEs will begin at the time of the first treatment visit and continue until the end of final study visit. All events will be followed to resolution or until the subject completes the study. A final assessment of outcome will be made at that time.

All AEs must be recorded in the subject's medical records and on the CRF. AEs will be reported using customary medical terminology along with the following information: the onset and end dates, whether the event is considered to be a SAE (see Section 9.3), the impact the event had on study treatment (see Section 9.2.1), the Common Terminology Criteria for Adverse Events (CTCAE) grade (intensity) of the event (see Section 9.2.2), the causality of the event (see Section 9.2.3), whether treatment was given as a result of the event (see Section 9.2.4), and the outcome of the event (see Section 9.2.5)

[figure not shown]

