This is a Phase 2, two-arm, randomized, double blind, placebo controlled multicenter study to evaluate the safety and efficacy of leronlimab (PRO 140) in patients with prolonged symptoms caused by COVID-19. Patients will be randomized to receive weekly doses of 700 mg leronlimab (PRO 140), or placebo. Leronlimab (PRO 140) and placebo will be administered via subcutaneous injection.

The study will have three phases: Screening Period, Treatment Period, and Follow-Up Period.

Screening Period (up to 1 week):

Screening assessments will commence at Visit 1 (V1) after obtaining signed informed consent, and will include review of medical and medication history, eligibility evaluation, vital signs, pulse oxygen saturation, physical examination, electrocardiogram (ECG), clinical symptom score assessment, and laboratory sample collection for routine serum biochemical, hematologic, coagulation, urinalysis, and urine pregnancy (if applicable). These assessments must be conducted within 7 days of the First Treatment Visit (V2).

All subjects who fail to meet eligibility criteria are considered screen failures, and are exited from the study without further evaluation.

Treatment Period (56 Days± allowed windows):

The schedule of visits during Treatment Period is as follows:

- Visit 2 (V2) [first treatment]: Within 1 week of the Screening Visit
- Visit 3 (V3): 3 (±1) days after V2
- Visit 4 (V4) [second treatment]: 7 (±1) days after V2
- Visit 5 (V5): 3 (±1) days after V4
- Visit 6 (V6) [third treatment]: 7 (±1) days after V4
- Visit 7 (V7): 3 (±1) days after V6
- Visit 8 (V8) [fourth treatment]: 7 (±1) days after V6
- Visit 9 (V9): 3 (±1) days after V8
- Visit 10 (V10) [fifth treatment]: 7 (±1) days after V8
- Visit 11 (V11): 3 (±1) days after V10

CONFIDENTIAL Page 7 of 101

Name of Sponsor/Company:		
CytoDyn, Inc.		
Name of Study Product:		
Leronlimab (PRO 140)		
Protocol Number: Indication:		
CD15_COVID-19	Coronavirus Disease 2019 (COVID-19)	

- Visit 12 (V12) [sixth treatment]: 7(±1) days after V10
- Visit 13 (V13): 3 (±1) days after V12
- Visit 14 (V14) [seventh treatment]: 7(±1) days after V12
- Visit 15 (V15): 3 (±1) days after V14
- Visit 16 (V16) [eighth treatment]: 7(±1) days after V14
- Visit 17 (V17) / End of Treatment (EOT) Visit: 7 (±1) days after V16.

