1.4.2.5. PRO 140 2301 Study

PRO 140 2301 was a multi-center, randomized, double-blind, placebo-controlled, parallel group study in 30 male and female adult subjects infected with HIV-1 [Jacobson, 2010]. Subjects were randomized to one of three groups (N=10/group), each receiving one of three treatments: (i) a single IV dose of 5 mg/kg by 30-minute IV infusion; (ii) a single IV dose of 10 mg/kg by 30-minute IV infusion; (iii) a single placebo dose by 30-minute IV infusion. The objective of the study was to assess and characterize the PK and PD of PRO 140 administered by IV infusion, assess efficacy at a new dosage level, and safety and tolerability of single doses of PRO 140.

All PRO 140-treated subjects had more than 10-fold reduction in viral loads [Jacobson, 2010]. Both the 5 mg/kg and 10 mg/kg doses have shown favorable tolerability and no dose-limiting toxicity has been observed. High levels of receptor occupancy (>85% reduction in the number of cells detected) were observed for 29 days after treatment with both 5 and 10 mg/kg doses.

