If Visit 2 (V2) takes place on the same day as the Screening Visit (V1), scheduled assessments performed under screening (V1) do not need to be repeated at V2. Subjects will be given a diary to record all symptoms daily throughout the entire treatment period starting at baseline.

Treatment Groups

IP Study Dosage **Dosing Frequency and Amount** Form concentration

Table 4-1:

Route of Drug Administration Parenteral 2 injections of PRO 140 (2 X 2 mL/inj.) PRO 140 175 mg/mLSC injection (700 mg)solution per week on opposite sides of abdomen 2 injections of placebo (2 X 2 mL/inj.) Parenteral 0 mg/mLSC injection Placebo solution per week on opposite sides of abdomen

At V2, subjects will be randomized to receive leronlimab (PRO 140) or placebo which will be administered subcutaneously weekly at V2, V4, V6, V8, V10, V12, V14, and V16.

The following assessments will be performed at V4, V6, V8, V10, V12, V14, V16, and V17(EOT): vital signs, pulse oxygen saturation, physical examination, electrocardiogram (ECG (V17 only), PROMIS® Fatigue Scale, PROMIS® Cognitive Function- Short Form 4a, PROMIS® Sleep Disturbance – Short Form 4a, Global Health Assessment (V17 only), blood sample collection for routine serum biochemical, hematologic, coagulation and urine laboratory assessments (V10 and V17). CD4+ and CD8+ T cell count and serum cytokine and chemokine levels (V10 and V17), assessment for the requirement of hospitalization and patient compliance to daily diary completion will be checked by the site staff.

Additionally, telephone or video contact visits will be performed 3 days (±1 day) after each treatment administration visit. The requirement of hospitalization and patient compliance to daily diary completion will be checked during V3, V5, V7, V9, V11, V13, and V15 via telephone.

Adverse events and concomitant medications will be monitored throughout the study.

Follow Up Period (4 weeks after EOT± 3 days)

Follow-up visit (V18) will be performed 4 weeks after the End of Treatment (EOT) visit. The following assessments will be performed at V18: vital signs, physical examination, pulse oxygen saturation, blood sample collection for immunophenotypic biomarker analysis, assessment for the requirement of hospitalization, review of adverse events and concomitant medications.

Note: During visits conducted at the study clinic, subjects and site personnel will use appropriate protective gear (e.g., masks, gloves) to prevent the spread of the infection.

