4.2.4. End of Treatment – EOT (V17)

The last visit during the treatment phase will be considered at the End of Treatment (EOT) visit. The assessments performed at this visit will include:

- Physical examination (see Section 7.5);
- Vital Signs (see Section 7.6),
- Pulse oxygen saturation (SpO2) (see Section 7.10);
- 12-lead electrocardiogram (see Section 7.11);
- Patient Symptom Diary (see Section 7.15);

Note: Patient compliance to daily diary completion will be checked by site staff.

- PROMIS® Fatigue Scale (see Section 7.16);
- PROMIS® Cognitive Function (see Section 7.17);
- PROMIS® Sleep Disturbance (see Section 7.18);
- Global Health Assessment (see Section 7.19);
- Collection of laboratory specimens (see Section 7.8) for
 - Complete blood count;

CONFIDENTIAL Page 52 of 101

- Biochemistry;
- Coagulation indices;
- O Urine pregnancy test, for female subjects of childbearing potential;
- Urine sample for urinalysis parameters;
- o CD4+ and CD8+ T cell count;
- Serum cytokine and chemokine levels;
- o CCR5 receptor occupancy; and
- Immunophenotypic biomarker analysis.
- Assessment for the requirement of hospitalization (see Section 7.12);
- Prior and concomitant medications assessment (see Section 7.7); and
- Review of adverse events (see Section 9).

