5.3. REMOVAL OF SUBJECTS FROM STUDY TREATMENT AND/OR STUDY AS A WHOLE

Subjects can be taken off the study treatment and/or study as a whole at any time at their own request, or they may be withdrawn at the discretion of the investigator for safety, behavioral or administrative reasons. In the case that a subject is removed from the study due to safety reasons, the FDA and other global regulatory authority will be notified. The reason(s) for discontinuation must be clearly documented on the appropriate eCRF and may include:

- Subject voluntarily withdraws from treatment (follow-up permitted)
- Subject withdraws consent (no follow-up permitted)
- Subject is unable to comply with protocol requirements

CONFIDENTIAL Page 54 of 101

- Subject experiences unacceptable toxicity
- Treating physician determines that continuation on the study would not be in the subject's best interest
- Subject becomes pregnant
- Subject becomes lost to follow-up (LTF)
- Subject will be withdrawn from the study if 2 consecutive doses of study drug are missed
- Subject manifesting Grade 4 or Grade 3 toxicity attributable to the Leronlimab (PRO 140)

If a subject fails to return for the scheduled study visit or is discontinued from the study, an attempt will be made to determine the reason(s). If the subject is unreachable by telephone, a registered letter will be sent to the subject requesting that he/she contact the clinic.

All patients with an ongoing SAE or AE attributable (definitely, probably, or possibly related) to the study treatment at the Post-Study (Follow-up) Visit (scheduled or premature) must be followed until the event is resolved (with or without sequelae) or deemed stable.

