9.4. REPORTING OF SERIOUS ADVERSE EVENTS (SAE)

The Investigator is required to report all SAEs that occur during the time period specified in Section 9.2. Once the Investigator becomes aware of an SAE, he/she must report the SAE to Medical Monitor within 24 hours.

The Medical Monitor may request additional supporting documentation as it becomes available, such as lab reports, ECG reports, discharge summary, hospital notes, etc, if applicable. Additional follow-up information as it becomes available must be reported to the Medical Monitor.

The Investigator is also responsible for reporting all SAEs to the appropriate Institutional Review Board (IRB) in accordance with local laws and regulations. The Investigator is responsible for maintaining documentation in the study file that indicates the IRB has been properly notified.

[figure not shown]

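### AE and SAE reporting stops at the final study visit, so subjects withdrawn from the study early have no guaranteed post-dose window for new events, yet count in full in crude AE percentages

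*Combined protocol and SAP*

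**What the plan says.** Protocol section 9.2 has the reporting of AEs and SAEs "begin at the time of the first treatment visit and continue until the end of final study visit". Section 9.4 adds: "The Investigator is required to report all SAEs that occur during the time period specified in Section 9.2". Neither mentions the last dose.

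For a subject who completes, the schedule supplies the interval. The synopsis gives "Visit 17 (V17) / End of Treatment (EOT) Visit: 7 (±1) days after V16", V16 being the eighth and last dose. Section 4 then states: "Follow-up visit (V18) will be performed 4 weeks after the End of Treatment (EOT) visit". The schedule of assessments puts windows of ±1 and ±3 days on these two steps.

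For a subject who does not complete, three places matter:

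- Section 5.3 covers removal from treatment, from the study, or both. One route stops treatment with follow-up permitted. Withdrawal of consent permits none. Two consecutive missed doses lead to withdrawal from the study. Patients with an ongoing SAE or an attributable AE "at the Post-Study (Follow-up) Visit (scheduled or premature) must be followed until the event is resolved" or is judged stable. The premature visit is given no date.
- Section 4.2.4 says: "The last visit during the treatment phase will be considered at the End of Treatment (EOT) visit". Section 4.3 places follow-up 28 (±3) days after EOT.
- Section 5.4 asks for every attempt at follow-up and sends withdrawals for an AE or SAE to the section 9 procedures. Section 9.5 requires known SAEs to be followed, including in discontinued subjects.

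In the SAP, the Safety Population (6.3) is everyone dosed. TEAEs (8.3.1) start at first treatment with no upper limit. Categorical summaries (8.1) are counts and percentages. Exposure is tabulated separately (8.1.5), and no AE rate per unit of time is planned.

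**The concern.** A safety window should follow exposure. Here it follows attendance, so it can be shortest for people who leave the study, while drug is still present. A new SAE ten days after a premature final visit falls outside the section 9.2 period, and section 9.4 then imposes no duty to report it.

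Two things are at stake. The first is ascertainment. The review triggers in section 5.2 turn on one or two reported events, and section 12 provides no data safety monitoring committee, so a single unreported late event could matter. The second is the comparison of arms. A subject seen for two weeks and one seen for twelve each add one to the denominator. If early withdrawal differs between arms, crude percentages compare unequal observation times.

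**Working it through.** **The plan's own timetable.** 7 + 56 + 28 = 91 days, as stated in the synopsis and SAP 2.3.

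**Days from last dose to final visit.**

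| Path | Arithmetic | Days |
|---|---|---|
| Completer, V16 to V18 | (7±1) + (28±3); nominal Day 84 − Day 49 | 31–39, nominal 35 |
| Stops on a dosing day, stays in the study, sections 4.2.4 and 4.3 taken to apply | 28±3 | 25–31 |
| Same reading, last treatment-phase visit is the second missed dosing visit | (12 to 16) + (25 to 31) | 37–47 |
| Withdrawn from the study; final visit is the second missed dosing visit | 2 × (7±1) | 12–16 |
| Leaves with an undated premature visit | none given | no minimum; 0 at the limit, if on a dosing day |

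Against completers, the fourth row is short by 31 − 16 = 15 to 39 − 12 = 27 days (nominally 35 − 14 = 21).

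**Is drug still present?** Section 1.4.1 gives a half-life of about 200 hours in monkeys; no human value is stated. Assuming first-order elimination and a similar human half-life, the fraction remaining after d days is 0.5^(24d/200):

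- 12 days: 37%; 16 days: 26%.
- 31 days: 7.6%; 35 days: 5.4%; 39 days: 3.9%.

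With an assumed half-life of 150 to 300 hours, 21–46% remains at 14 days and 2–14% at 35 days. In humans, section 1.4.2.5 reports that high levels of receptor occupancy "were observed for 29 days after treatment with both 5 and 10 mg/kg doses". Those were single intravenous doses, so they support persistence in general, not a figure for this regimen.

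**Do the other provisions fill the gap?** The last paragraph of 5.3 and section 9.5 concern events that already exist. Section 5.4 sets no duration, and its pointer to section 9 leads back to the 9.2 window. The one reporting rule counted from the last dose is pregnancy notification, at 30 days (9.5). None sets a minimum period for detecting new events.

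**Effect on crude percentages (illustration).** Assume a constant hazard, a true 84-day AE risk R, and a fraction f of an arm whose final visit is on Day t. Then λ = −ln(1 − R)/84, and the observed percentage is (1 − f)R + f(1 − e^(−λt)). The values R = 34% and 50% match the proportions with any AE in the two arms of CD10 (section 1.4.2.18) and are borrowed only for scale.

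- R = 34%: f = 10%, t = 35 gives 32.2%; f = 30%, t = 7 gives 24.8%.
- R = 50%: f = 10%, t = 35 gives 47.5%; f = 30%, t = 7 gives 36.7%.

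**Would a longer window alone cure this?** No. Take f = 30%, all last dosed on Day 0 with a final visit on Day 7. Extending reporting to Day 35 moves the observed figure from 24.8% to 28.6%, still below 34%. Likewise a subject last dosed on Day 14 would be observed to Day 49, against Day 84 for a completer.

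**The case against.** The strongest reply is that sections 4.2.4 and 4.3 already deal with early stoppers. If the last treatment-phase visit serves as EOT, V18 follows 25 to 31 days later and the gap largely closes. This stands for subjects who stop dosing and stay in the study, although the text does not say so outright. It does not reach a subject withdrawn from the study, and section 5.3 separately foresees a premature follow-up visit without dating it.

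A reader might also infer that early leavers go mainly because of toxicity, so that the most informative subjects are lost. The documents do not support that. Toxicity is one of several reasons in section 5.3, with no frequencies. The toxicity tables in 6.1.5 end study treatment, not participation, so such subjects may be observed to V18. Section 5.4 also directs withdrawals for an AE or SAE to the section 9 procedures.

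Nor can the number affected be stated. The plan gives no dropout rate, and an assumed rate would include subjects who withdraw consent and cannot be followed. Zero days is a limiting case, not what early leavers generally receive. Finally, observed incidence is lowered only when a subject's first event falls in the unobserved interval.

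**Conclusion.** The point holds in limited form. Completers are adequately covered. Subjects who stop dosing but stay in the study may be covered, depending on how 4.2.4 and 4.3 are read. Subjects withdrawn from the study have no minimum post-dose window for new AEs or SAEs. They have 12 to 16 days in the two-missed-doses case, 15 to 27 fewer than completers, and possibly less with a premature visit. The planned percentages still count them in full.

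The day counts follow from the schedule alone, given where the final visit falls. The residual-drug figures (26–37% at 12–16 days, 4–8% at 31–39 days) rest on a monkey half-life and are indicative only. The dilution figures are an illustration under assumed hazard and dropout. Bias between arms would require withdrawal to differ by arm, which cannot be known in advance. The gap concerns how completely safety events are ascertained in a 50-subject exploratory trial, and is worth closing because doing so is simple.

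**What to change.** In protocol 9.2, end AE and SAE reporting at V18. For any dosed subject who stops treatment or leaves early and has not withdrawn consent to follow-up, end it no sooner than the later of the final visit and a fixed interval after the last dose. Thirty-five days matches the nominal completer interval (Day 49 to Day 84); the sponsor may choose another length. Collect by telephone where no visit takes place. Section 9.4 follows without further change.

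In SAP 8.3.1, list subjects whose window was cut short, with the reason. Add AE and SAE summaries per person-time beside the crude percentages, because the longer window does not by itself equalise observation time.

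The cost is one telephone contact per early leaver, one added summary and listing, and a protocol amendment with IRB approval, possibly with a consent form revision (section 11.3). No clinic visit or sample is added, and no dosing or treatment rule changes.

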9.2.1. Impact on Study Treatment

The impact the event had on the study treatment will be assessed as either: dose increased, dose not changed, dose rate reduced, dose reduced, drug interrupted, drug withdrawn, not applicable, or unknown. The "not applicable" assessment will be used only when the subject is no longer in the Treatment Phase of the protocol.

9.2.2. CTCAE Grade (Intensity) Assessment

The guidelines outlined in CTCAE v5.0 will be used for assessing the intensity of the event (See Appendix 17.2). The general guidelines for assessing the AE grade appear below. Full guidelines may be obtained at

CONFIDENTIAL Page 75 of 101

https://ctep.cancer.gov/protocolDevelopment/electronic applications/docs/CTCAE v5 Quick Re ference 8.5x11.pdf

Table 9-1: CTCAE v5.0 General Guidelines

Grade	Description
Grade 1	Mild; asymptomatic or mild symptoms; clinical or diagnostic observations only; intervention not indicated.
Grade 2	Moderate; minimal, local or noninvasive intervention indicated; limiting age-appropriate instrumental activities of daily living (ADL)*.
Grade 3	Severe or medically significant but not immediately life-threatening; hospitalization or prolongation of hospitalization indicated; disabling; limiting self care ADL†.
Grade 4	Life-threatening consequences; urgent intervention indicated.
Grade 5	Death related to AE.

^{*}Instrumental ADL refer to preparing meals, shopping for groceries or clothes, using the telephone, managing money, etc.

-Common Terminology Criteria for Adverse Events (CTCAE), v5.0: November 27, 2017

9.2.3. Causality Assessment

AEs will be assigned a relationship (causality) to the study treatment. The Investigator will be responsible for determining the relationship between an AE and the study treatment. The type of event, organ system affected, and timing of onset of the event will be factors in assessing the likelihood that an AE is related to the study treatment. Relationship of AEs to study treatment will be classified as follows:

- 1. Definitely related: This category applies to those AEs that the Investigator feels are incontrovertibly related to the study treatment. An AE may be assigned an attribution of definitely related if or when it meets all of the following criteria: (1) it follows a reasonable temporal sequence from administration of the study treatment; (2) it could not be reasonably explained by the known characteristics of the subject's clinical state, environmental or toxic factors, or other modes of therapy administered to the subject; (3) it follows a known response pattern to treatment with the study treatment.
- 2. Probably related: This category applies to those AEs which, after careful medical consideration at the time they are evaluated, are felt with a high degree of certainty to be related to the study treatment. An AE may be considered probable if or when (must have three): (1) it follows a reasonable temporal sequence from administration of the study treatment. (2) It could not readily have been produced by subject's clinical state, environmental or toxic factors, or other therapies administered to the subject. (3) Disappears or is decreased upon discontinuation of the study treatment. (4) It follows a known response pattern to treatment with the study

CONFIDENTIAL Page 76 of 101

[†]Self care ADL refer to bathing, dressing and undressing, feeding self, using the toilet, taking medications, and not bedridden.

treatment.

- 3. Possibly related: This category applies to those AEs which, after careful medical consideration at the time they are evaluated, are judged unlikely but cannot be ruled out with certainty to the study treatment. An AE may be considered possible if or when (must have two): (1) it follows a reasonable temporal sequence from administration of the study treatment. (2) It could not readily have been produced by subject's clinical state, environmental or toxic factors, or other therapies administered to the subject. (3) Disappears or is decreased upon discontinuation of the study treatment. (4) It follows a known response pattern to treatment with the study treatment.
- **4.** Unlikely related: In general this category can be considered applicable to those AEs which, after careful medical consideration at the time they are evaluated, are judged likely to be unrelated to the study treatment. An AE may be considered unlikely if or when (must have two): (1) it does not follow a reasonable temporal sequence from administration of the study treatment. (2) It could not readily have been produced by subject's clinical state, environmental or toxic factors, or other therapies administered to the subject. (3) Disappears or is decreased upon discontinuation of the study treatment. (4) It does not follow a known response pattern to treatment with the study treatment.
- **5.** Unrelated: This category applies to those AEs which, after careful consideration at the time they are evaluated, are clearly and incontrovertibly due to extraneous causes (disease, environment, etc.) and determined with certainty to have no relationship to the study treatment.

